Anesthesia will be maintained with 1 MAC sevoflurane, additional fentanyl and rocuronium will be given per anesthesia discretion. Quantity of all anesthetic and analgesic medications during the operation will be documented. Local 0.25% bupivacaine (10mL) without epinephrine injection will be used post-operatively during closure in all patients regardless of being in the study group or control group as a part of normal operational procedure. Reversal of neuromuscular blockade will be with sugammadex 2 mg/kg. When standard extubation criteria are met the subject will be extubated and transported to PACU.

Intervention

Fifteen minutes following endotracheal intubation, subjects will be intravenously infused with either 0.8% lidocaine at 1 mg/kg/h if < age 65 and 0.5 mg/kg/h if ≥ age 65 or an equal volume and rate of normal saline placebo as determined by the randomization table. The infusion will be continued for 24 hours after surgery. Masked infusion bags of 0.8% lidocaine or normal saline will be prepared by the Investigational Pharmacy at the University of Missouri Hospital according to the subject randomization table. Infusion preparation will occur in a blinded fashion to all clinical and research personal involved with the study case. To maintain blinding, the investigational pharmacist will enter "Study Medication" in the medical record.

In PACU patient will receive additional fentanyl or hydromorphone. Postoperative pain scores, vital measures, and opioid use will be documented. Once patient is able to tolerate oral intake, they will be switched to oral narcotics. Patient fentanyl consumption and 10 cm visual analog scale (VAS) will be utilized. VAS will be scored from a 0 "no pain" to a 10 "worst pain ever" and will be recorded by blinded research staff at 1, 2, 4, 6, 12, 24 hours post-operatively, postop day 2, any additional day during hospitalization, at time of discharge and 14-day follow up. The nurse that will be caring for these patients will document the time of first bowel movement, return of flatus and any adverse reactions per standard of care. Post-Anesthesia Patient Satisfaction Assessment will be performed at 24 h post-surgery.

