Two statistical analysis methods will be used to make a comparison between the two treatment groups with regard to the primary end point: (i) to assess the difference of pain level between the two groups at specific time point, Wilcoxon Rank Sum Test will be used, (ii) to assess the pattern of change in pain level over the study period between the two groups, a Generalized Estimation Equation (GEE) model will be used.

Sample Size					Drop-out Inflated Enrollment	
Treatment	Placebo	Effect Size	SD	Power	Treatment	Placebo
20	20	2	2	80%	23	23
27	27	2	2	90%	30	30

*A dropout rate of 10% was considered here. A Two Sample T-test using effect size sample size method was used to get an estimate of the samples needed from the PASS program.

Table 2: Sample size assuming 80% and 90% power.

RESEARCH PARTICIPANT REGISTRATION AND RANDOMIZATION PROCEDURES

Research Participant Registration

Confirm eligibility as defined in the section entitled Criteria for Patient/Subject Eligibility.

Obtain informed consent, by following procedures defined in section entitled Informed Consent Procedures.

Randomization

Randomization will be accomplished by the method of random permuted block and stratified by the type of the surgery and subject age. Since this is a double-blind study, the subjects' treatment assignments will be kept in a blinded randomization table. The Excel column containing treatment designation assigned by a biostatistician will be occluded from view to maintain blinding. The investigational pharmacist will not be blinded and will have the randomization table. After recruitment, research staff will randomize the patient into the correct stratification and the Investigation Pharmacy will be notified. If it is clinically necessary to unblind a subjects' treatment allocation this will be done using the randomization table.

DATA MANAGEMENT ISSUES

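### The allocation list is kept from the staff who randomise only by an occluded Excel column, although the trial already has an unblinded pharmacist who could hold it alone

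*Combined protocol and SAP*

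**What the plan says.** The combined protocol and SAP covers allocation in its Randomization section. On the method: "Randomization will be accomplished by the method of random permuted block and stratified by the type of the surgery and subject age". No block size is given. Assignments sit in a table, and one step is named to keep it blind: "The Excel column containing treatment designation assigned by a biostatistician will be occluded from view to maintain blinding".

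On who does what: "After recruitment, research staff will randomize the patient into the correct stratification and the Investigation Pharmacy will be notified". On the pharmacy: "The investigational pharmacist will not be blinded and will have the randomization table". If a subject must be unblinded for clinical reasons, the section points to the table again ("treatment allocation this will be done using the randomization table").

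The Design section lists research staff among those blinded. The Intervention section says that pain scores "will be recorded by blinded research staff at 1, 2, 4, 6, 12, 24 hours post-operatively", and then at later times that include discharge. The Sample Size section makes pain at discharge the primary outcome.

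The Data Management section stores study data on a secure departmental server and limits study files to members of the research team. No section mentions a central or web system, sealed envelopes, a password on the list, a coded staff copy or an access log.

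**The concern.** Allocation concealment means that the person entering a patient cannot know the next assignment. Masked bags do a different job: they protect blinding after assignment. Here the list appears to be prepared in advance, the people who randomise are people who must stay blind, and the one stated barrier is that a column is out of view.

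An assignment known ahead of time could influence which patient is approached or entered, and when. An assignment known afterwards could influence discretionary withdrawal. The section on criteria for removal allows withdrawal when it is judged to be in the patient's best interest, and excludes from analysis subjects whose infusion is stopped or whose primary endpoint is missing. With 20 evaluable patients planned per arm, few patients need be affected for balance between the arms to suffer.

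**Working it through.** No calculation decides this point; it turns on reading the sections together. The arithmetic in steps 1, 4 and 5 only gives scale.

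**1. The plan's own figure.** The only computed figure is the sample size. Inputs from the Sample Size section and Table 2: difference 2, SD 2, two-sided 5% level, 80% power, 10% dropout. An exact t-test needs 17 per arm. Dividing by 0.864, the minimum efficiency of the Wilcoxon test (my assumption about the option used), gives 17 / 0.864 = 19.7, so 20. Inflation gives 20 / (1 − 0.10) = 22.2, so 23 per arm and 46 in all. These match the plan. Better concealment does not change them.

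**2. The roles side by side.**
- The biostatistician assigns the treatment designations.
- The investigational pharmacist is unblinded and has the table; the pharmacy prepares every bag from it.
- Research staff randomise into the stratum and must stay blinded.
- Research staff record the pain scores.

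The first two need not be kept from the assignments, so the column can only be occluded for someone else. The natural reading is that research staff work from that file. This is an inference: the text states neither the copy they use nor how the column is occluded.

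**3. Does another safeguard close the gap?** The secure server does not, because it admits the research team, which includes the people to be kept from the list. The masked bags and the neutral chart entry act after assignment. Randomising after consent narrows the opening for selection but does not close it while a list exists in advance.

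**4. What a partial view would give away.** Suppose only past assignments in a stratum became known. With fixed blocks of size B and 1:1 allocation, the share of assignments that can then be predicted with certainty is 1 / (B/2 + 1):
- B = 2: 50%
- B = 4: 33%
- B = 6: 25%

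The block size is not stated, so this is a range over assumed values. It shows that rows already used need protecting as well as rows still to come.

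**5. How sensitive a trial of this size is.** Assume no true effect, 20 per arm, SD 2, a two-sided 5% t-test (used here in place of the Wilcoxon test) and a bias that shifts the arms apart by d points. The non-centrality is d / (2 × √(2/20)) = d / 0.632.

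| d (points) | d / 0.632 | Rejection rate |
|---|---|---|
| 0.25 | 0.40 | 6.7% |
| 0.50 | 0.79 | 12.0% |
| 0.75 | 1.19 | 21.2% |
| 1.00 | 1.58 | 33.8% |

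The shifts are assumed. The table does not estimate the bias in this trial; it shows what a shift of each size would do to the 5% error rate.

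**The case against.** The strongest reply is that the plan may already work as it should. Staff supply the stratum, the pharmacy is notified, and the pharmacist, who has the table, prepares the bag. On that reading staff never open a file with treatments in it, and only the description is thin. This is possible, and it is why the point concerns a weak stated method and not a failure. It leaves the occluded column unexplained, however: if staff never open the file, nothing needs to be hidden from them.

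Other safeguards stand. Randomisation follows written consent. The Recruitment Plan introduces the study to every eligible scheduled patient, which leaves less room to choose among them. Patients, clinicians and nurses are blinded.

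A reader might go further in three ways that the documents do not support:
- That staff can simply unhide the column. The text does not say whether it is hidden, locked or removed from a staff copy.
- That the person who randomises also scores. Research staff is a group label; the plan states neither overlap nor separation.
- That scoring is as exposed as selection. To sway a score, someone would have to learn the assignment and then influence or misrecord the rating of a blinded patient on a masked infusion.

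**Conclusion.** The point holds as a weakness in the stated method of concealment. The occluded column is the only device named for keeping the list from those who randomise, and the trial already has the person and workflow for a stronger one.

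The main exposure is foreknowledge of the next assignment, through selection and timing of entry, together with discretionary withdrawal once an assignment is known. Assessment bias comes second. Nothing in the documents shows that any assignment was or will be revealed, and any figure for the share of patients steered would be invented, so the size of the bias cannot be given. The sample size is untouched.

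The conclusion rests on two readings: that the list is prepared in advance, and that people other than the pharmacist can open the file with the occluded column. If the second is wrong, the same change still serves as a clarification. It is a cheap improvement and not a defect that invalidates the design.

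**What to change.** Replace the occluded-column sentence in the Randomization section with a procedure along these lines:
- The biostatistician sends the list with treatments only to the investigational pharmacist.
- After consent, research staff send the pharmacist the subject number and stratum.
- The pharmacist takes the next unused assignment in that stratum and logs the date and time.
- Any file available to research staff has no treatment column, for past or future subjects.

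Two sentences need to agree with this. The provision for emergency unblinding should name the pharmacist's table and say how it is reached outside pharmacy hours. The strata should also be settled, because the Design section stratifies by surgery type alone while the Randomization section adds age.

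The cost is a short text change and a small logging task for the pharmacist. No new staff or system is needed, and the log would let the sponsor document how each assignment was issued.
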